3.3 Exploratory Outcome Measures

- I. Change from baseline to week 26 in HOMA-IR.
- II. Change from baseline to week 26 in LDL, HDL, non-HDL cholesterol, and triglycerides.
- III. Change from week 26 to week 38 in systemic inflammation markers (IL-6, IP10, sCD163, sTNF-RI, oxidized LDL, and KT ratio).
- IV. Gastrointestinal microbial diversity from fecal samples at entry and post-entry visits. [*Not analyzed at SDAC*]
- V. Change in gastrointestinal symptoms from baseline to 26 weeks.
- VI. Diversity of gut microbiome and dietary intake composition. [Not analyzed at SDAC]

4 Statistical Methods

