# 6.0 CLINICAL AND LABORATORY EVALUATIONS

# 6.1 Schedule of Events

		Entry Week 0	Post-Entry								
Evaluation (Within 4) days prio	Screening		Week 2 ±7days	On Treatment Post Treat. (Weeks) (Weeks)					10.25	Conf. of	Prem.
	(Within 45 days prior to entry)			4	6	1 4	2 5	26	38	Virologic Failure	Study DC
	,,,,,,,,,,,,,,,,,,,,,,,,,,,,,,,,,,,,,,,		iruays		±7 days			±7 days			
Documentation of HIV	Х										
Medical History/ Medication History	Х		Х								
Targeted Physical Exam	Х		Х		Х	Х		Х	Х		Х
Height	Х		i i				-				
Weight	Х		2					Х	X		
Clinical Assessments			Х		Х	Х		Х	Х		х
Dietary Assessment		z	Х		Х	Х		Х	Х		
Sexual Activity Assessment			Х		Х	Х		Х	Х		
Bowel Symptom Assessment			Х		Х	,		Х			
Fatigue Symptom Assessment			Х			Ÿ		Х			
Dispense Study Products			Х			Х					
Hematology	Х		X			X		Х	X		
Liver Function Tests	Х		Х			Х		Х			7
Blood Chemistries	Х		Х			X		Х			
Calculated CrCl	Х										
Fasting Lipid Profile			Х			Х		Х			
Pregnancy Testing	Х	Х	·s		lf		nanc				
Hepatitis Serology	Х	5									
CD4+/CD8+	Х		Х			Х		Х	×		
Stored Plasma for sCD14		Х	Х		Х	Х	Х	Х	Х		Х

		-	8		F	Post-E	ntry				1.
Screening Evaluation (Within 45 days prior	Screening	Entry Week 0		On Treatment (Weeks)					Post Treat. (Weeks)	Conf. of	Prem.
			Week 2 ±7days	4	6	1 4	2 5	26	38	Virologic Failure	Study DC
			_rudy3			±7 da	iys		±7 days		
Stored Plasma for Soluble Markers of Inflammation, Coagulation, Immune Activation, and Gut Epithelial Barrier Integrity		х	×		X	х	х	X	х		
Stored Plasma for Insulin Resistance			Х		i i	Χ		Х			er e
Stored Plasma for Kynurenine to Tryptophan Ratio			х		8			х			
Stored peripheral blood mononuclear cells (PBMCs) for Monocyte and T- cell Phenotyping			x			x		х	x		
Stored Plasma for Enterocyte Death (I-FABP)			х		X	X	X	Х	X		
Stored PBMC for Future Analysis			Х		Х	Х		Х	Х		
Stored Plasma for Future Analysis			Х		Х	Х	5	Х	Х		
Plasma HIV-1 RNA	Х		Х			X		Х		Х	х
Fecal Sample and Rectal Swabs			Х		Х	Χ		Х	Х		
Telephone Assessment				Х							
Adherence Assessment					X	X		Х			Х
Empty Sachet Count					Х	Х		Х			Х

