# Stored Plasma for Soluble Markers of Inflammation, Coagulation, Immune Activation, and Gut Epithelial Barrier Integrity

Plasma specimens for measurement of IL-6, IP10, sCD163, TNF-RI, D-dimer, LPS, LBP, and oxidized LDL will be collected and stored for batch analysis at the end of the study. For storage and shipping, please see the A5350 LPC.

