#### Stored Plasma for Kynurenine to Tryptophan Ratio

Plasma specimens will be collected and stored for batch analysis at the end of the study. For storage and shipping, please see the A5350 LPC.

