#### Stored Specimens

PBMCs and plasma will be stored for future analysis. For storage and shipping, please see the A5350 LPC.

Specimens will be stored for possible future genetic testing.

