# 9.2.3 Exploratory Outcome Measures

- 9.2.3.1 Change from baseline to week 26 in HOMA-IR.
- 9.2.3.2 Change from baseline to week 26 in LDL, HDL, non-HDL cholesterol, and triglycerides.
- 9.2.3.3 Change from week 26 to week 38 in systemic inflammation markers (IL-6, IP10, sCD163, sTNF-RI, oxidized LDL, and KT ratio).
- 9.2.3.4 Gastrointestinal microbial diversity from fecal samples at entry and postentry visits.
- 9.2.3.5 Change in gastrointestinal symptoms from baseline to 26 weeks.

9.2.3.6 Assess diversity of gut microbiome based on dietary recall.

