#### 9.6.2 Secondary Analyses

Similar to the initial primary analysis regression model, changes in other outcome measures will be compared between the Visbiome Extra Strength and placebo arms by linear regression. For these models each participant will have a single outcome measure of change from baseline to week 26. The only predictor variable will be study arm.

The weeks 26 and 38 levels of the primary, secondary, and exploratory outcome measures will be compared with baseline levels through linear regression.

Spearman correlations will be used to evaluate correlations between changes in select outcome measures. In addition, longitudinal changes in these measures will be examined using graphical approaches, descriptive statistics, and possibly repeated measures modeling.

Safety will be evaluated by summarizing the nature and rate of AEs within each study arm for all participants initiating study product. Comparisons of overall and AE-specific grades between study arms will be evaluated with an exact test for ordered categorical data (Wilcoxon rank-sum test of the maximum grade for each participant). Study product tolerability will be evaluated by summarizing study product modifications and discontinuations by study arm.

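### KT ratio is listed in the week 26 to week 38 exploratory outcome, but neither the protocol nor the SAP plans a KT measurement at week 38

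*SAP*

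**What the plan says.** **The outcome.** SAP 3.3 item III reads "Change from week 26 to week 38 in systemic inflammation markers (IL-6, IP10, sCD163, sTNF-RI, oxidized LDL, and KT ratio"). Protocol 9.2.3.3, which opens "Change from week 26 to week 38 in systemic inflammation markers", names the same six markers, KT ratio included. It serves the durability objective in protocol 1.6.5.

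**The KT specimen.** In the protocol 6.1 Schedule of Events, KT has a separate row, "Stored Plasma for Kynurenine to Tryptophan Ratio", marked at week 2 and week 26 and at no other visit. The matching instruction in 6.3.15 says only "Plasma specimens will be collected and stored for batch analysis at the end of the study" and refers storage and shipping to the laboratory processing chart (LPC). It names no visit.

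**Other plasma drawn at week 38.** The soluble-marker row is marked at week 38, and its assays are fixed in 6.3.15: "Plasma specimens for measurement of IL-6, IP10, sCD163, TNF-RI, D-dimer, LPS, LBP, and oxidized LDL will be collected". KT is not among them. A further row, "Stored Plasma for Future Analysis", is also marked at week 38. Its stated purpose is general: "PBMCs and plasma will be stored for future analysis".

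**The analysis text.** Protocol 9.6.2 adds a blanket sentence: "The weeks 26 and 38 levels of the primary, secondary, and exploratory outcome measures will be compared with baseline levels through linear regression".

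**The concern.** A change from week 26 to week 38 needs a value at each end. For KT the schedule supplies only the first. A laboratory that assayed exactly what the schedule assigns to KT would run two visits per participant and return nothing for week 38.

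Two things would be at stake. A marker named in advance in both documents could go unreported without anyone having decided to drop it. Alternatively, the decision to assay KT at week 38, or not, could be taken late and informally. KT is not incidental to the rationale: protocol 2.1 cites a fall in plasma KT ratio in SIV-infected macaques given the product. Whether any such effect lasts off product is what this component was meant to describe.

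**Working it through.** There is no stated figure to reproduce. The check compares visits with assays.

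**Step 1: read the schedule by column.** Each row in the table below splits into the same 12 fields: the row label, screening, entry, weeks 2, 4, 6, 14, 25, 26 and 38, confirmation of virologic failure, and premature discontinuation.

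| Row in protocol 6.1 | Visits marked | Week 38? |
|---|---|---|
| KT ratio plasma | 2, 26 | No |
| Soluble-marker plasma | Entry, 2, 6, 14, 25, 26, 38 | Yes |
| I-FABP plasma | 2, 6, 14, 25, 26, 38 | Yes |
| PBMC phenotyping | 2, 14, 26, 38 | Yes |
| Plasma for future analysis | 2, 6, 14, 26, 38 | Yes |

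A stray character in the KT row falls in the week 6 column, not week 38. The neighbouring rows show their week 38 marks where expected, so the empty KT cell is not explained by a shifted column.

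**Step 2: match the six markers to an assigned specimen at both visits.**

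| Marker | Assigned specimen | Week 26 | Week 38 |
|---|---|---|---|
| IL-6 | Soluble-marker plasma | Yes | Yes |
| IP10 | Soluble-marker plasma | Yes | Yes |
| sCD163 | Soluble-marker plasma | Yes | Yes |
| TNF-RI | Soluble-marker plasma | Yes | Yes |
| Oxidized LDL | Soluble-marker plasma | Yes | Yes |
| KT ratio | Own row | Yes | **No** |

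Five of six markers can be computed. KT has 0 planned week 38 specimens.

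**Step 3: look for text that fills the gap.** Clarification Memo #1 and Letter of Amendment #1 add no week 38 KT draw. SAP 2.10 records both, and SAP 3.3 still lists the outcome. The SAP 4.3 windows cannot supply a value either: the week 25 and 26 window is weeks [23, 28] and the week 38 window is [36, 40]. They do not overlap, so a week 26 KT result cannot count as week 38.

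**Step 4: check what else uses KT.** The secondary outcome in protocol 9.2.2.1 and SAP 3.2 needs baseline and week 26. KT plasma is marked at week 2 (pre-treatment) and at week 26, so that outcome stands.

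**Step 5: size the repair.** With 90 participants, the schedule implies at most 90 × 2 = 180 KT assays. Adding week 38 makes at most 90 × 3 = 270, an increase of at most 90.

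**The case against.** The strongest reply is that no data need be lost. Plasma is stored at week 38, stored specimens are assayed only after follow-up ends (SAP 2.11.2), and the choice of tube can be made late. That is right, and it rules out a stronger reading that a reader might infer: that week 38 KT is unavoidably missing for everyone. The documents show a specimen that has not been assigned, not one that cannot exist. But the same point does not make the measurement planned, because no sentence in the protocol or SAP directs that plasma to KT.

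Second, the LPC was not available for this review and may allocate the tube. This stands as a limit: the finding concerns the protocol and SAP only.

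Third, a reader might count protocol 9.6.2 as a second specific KT analysis that fails. It does not name KT. Read literally, its blanket wording would also require week 38 insulin resistance, fasting lipids and bowel symptoms, none of which is marked at week 38. The natural reading is that it applies where a measure was taken, so it adds little independent evidence.

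Fourth, the schedule was read from an extracted table with damaged headers. The consistent field count makes a misread unlikely, and a glance at the original page will settle it.

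Finally, this is one component of an exploratory outcome. That is true, and it limits the importance of the point without removing the inconsistency.

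**Conclusion.** The point holds as an inconsistency between an outcome list and the schedule. On the protocol and SAP as written, the KT change from week 26 to week 38 cannot be computed, because no KT measurement is planned at week 38. The size is one of six markers in one exploratory outcome.

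It would be wrong to infer that the durability outcome fails as a whole. The primary sCD14 outcome, the sample size and safety are also untouched.

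The conclusion rests on two assumptions: that the extracted KT row reflects the printed one, and that no document outside those reviewed, such as the LPC, already assigns week 38 plasma to KT. If the LPC does so, the remedy reduces to stating it in the SAP. The point is minor in consequence but worth settling before the batch assay, when it is still cheap.

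**What to change.** Before the end-of-study batch assay, choose one of these and record it:

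1. **Keep KT, using stored plasma.** State in the SAP that KT will be assayed on the week 38 plasma stored for future analysis. First confirm that its volume and handling suit the assay, which the documents do not say.
2. **Keep KT, with its own specimen.** Add a week 38 mark to the KT row in protocol 6.1. This helps only participants who have not yet had that visit.
3. **Drop KT from this outcome.** Remove it from protocol 9.2.3.3 and SAP 3.3 item III, and limit the general week 38 comparison in protocol 9.6.2 to measures collected at week 38. Without that limit, the blanket wording would still reach week 38 KT.

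The first two options cost one extra KT assay per participant, and the second also needs a schedule change. The third costs one exploratory marker and brief edits to both documents.

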4.1 Analysis Populations

Intent-To-Treat (ITT): All randomized participants.

Modified Intent-To-Treat (mITT): All randomized participants who started study product.

Per-Protocol (PP): All eligible, randomized participants who 1) have baseline and week 25/26 sCD14 measurements, 2) remain on study product through week 26 (participants with more than 50% on average of missed study product may be excluded), 3) have not used prohibited medications, 4) do not have a confirmed virologic failure (as defined per section 6.2.3 at or prior to week 26, and 5) do not experience inflammatory conditions, receive vaccines, or have concurrent illness (as defined per section 6.2.3).

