# 9.6 Analyses

All statistical tests will be two-sided with a nominal alpha level of 0.05. Because this is a phase II study and all potential biologic activities of the intervention are of interest, analyses will be as-treated, and limited to participants who 1) have baseline and week 26 sCD14 measurements, 2) remain on study product through week 26 (participants with more than 50% on average of missed study product may be excluded), 3) have not used prohibited medications, 4) do not have a confirmed virologic failure (as defined per section 6.2.3 at or prior to week 26, and 5) do not experience inflammatory conditions, receive vaccines, or have concurrent illness (as defined per section 6.2.3).

NOTE: Participants experiencing inflammatory conditions at the time of a visit are instructed to wait 7 days before measurements are obtained. Measurements obtained while inflammatory conditions are present will not be included in the analysis. A supplemental intent-to-treat analysis will also be performed and will include all randomized participants. No adjustment for multiple testing will be performed. A summary of the number of participants experiencing study product-related AEs and the types of AEs will be reported, as will the proportion of participants who discontinue study product after entry.

To reduce intra-participant variability, two blood draws will be performed at baseline (entry and week 2) and week 26 (week 25 and week 26) and the measurements will be the average of two for sCD14. If repeat measurements are not available at either of these time points, a single measurement will be used rather than the average.

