4.3 Analysis Visit Windows

For all analyses, the following visit windows will be used:

- Screening: evaluations completed within 45 days of randomization.
- Entry (week 0): entry evaluations must occur on/after randomization and at least 24 hours after screening.
- Week 2: pre-treatment evaluation scheduled within a week [1, 3] window but prior to treatment initiation, treatment must begin within the next 72 hours after evaluation.
- On-treatment evaluations:
 - Week 4: weeks (3, 5]
 - Week 6: weeks (5, 8]
 - Week 14: weeks [12, 16]
 - Week 25 & 26: weeks [23, 28]
- Week 38: post-treatment evaluation scheduled within a week [36, 40] window.

If multiple results are available within the Week 6 or 14 visit windows the result closest to the scheduled visit will be used. If multiple results are available within the Week 38 window the result closest to 12 weeks after the last dose of study treatment (corresponding to protocol-defined 12 week washout) will be used.

Results within the weeks [23, 28] visit window will use the following logic to determine Week 25 and Week 26 results:

- If two results are collected on treatment the earlier will be Week 25 and the latter Week 26.
- If two results are collected off treatment the earlier will be Week 25 and the latter Week 26.
- If one result is collected on treatment and one result is collected off treatment the on treatment will be Week 25 and the off treatment Week 26.
- If only one result is collected it will be Week 25.
- If three or more results are available priority will be given to those collected on treatment and assigned Weeks based on the above rules.

For markers run in duplicate at entry and Week 2 and also at Weeks 25 and 26, "baseline" will refer to the average of entry and Week 2 and "Week 25/26" will refer to the average of Week 25 and Week 26. If only one result is available at either of these time points the single result will be used. For per-protocol analyses the "Week 25/26" calculation will only use results collected while on treatment.

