4.4 Statistical Summaries and Testing

All statistical tests will be two-sided with a nominal alpha level of 0.05 and no adjustment for multiple testing.

Specimens collected 1 day after the last dose of study treatment will be considered "on treatment".

Specimens collected within 6 days of an influenza vaccination will not be used for analysis unless the vaccination and specimen collection occurred on the same date and the site has documented that the vaccination was given after specimen collection.

Outcome measures will be transformed for analyses and summaries on the log₁₀ scale, as appropriate, if determined to not be approximately normally distributed.

Because the stratification is to ensure balance between the treatment arms within A5352s and is not felt to affect A5350 outcomes, the stratification will not be taken into account in analyses.

Safety analyses will summarize the highest grade AE by participant using the mITT population and will compare treatment arms using the Wilcoxon rank-sum test. All AEs and AEs related to study treatment will be analyzed.

For all continuous outcome measures, tabular and graphical data summaries will be provided for both cross-sectional values across study weeks and change from baseline to post-baseline study weeks and will use the PP population. Mean changes in outcome measures will be compared between arms with either a two-sample t-test with equal variances or an adjusted linear regression model, as appropriate. The mean difference and 95% confidence interval (CI) will be provided along with the associated p-value.

For the primary analysis, two supplemental linear regression analyses will be performed. The first will additionally adjust for baseline sCD14 values (continuous) while the second will assess differential Visbiome Extra Strength

effects by baseline sCD14 tertile by additionally adjusting for the sCD14 tertile main effect and the study arm by sCD14 tertile interaction.

Correlations will be assessed with scatter plots as well as the Spearman correlation coefficient and associated p-value using the PP population.

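### Per-protocol criterion 1 requires sCD14 results, so a participant with no usable sCD14 at baseline or at week 25/26 drops out of every continuous outcome and correlation; the loss is probably small and cheap to avoid

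*SAP*

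**What the plan says.** SAP 4.1 lists five conditions for the PP set. The first is that participants "have baseline and week 25/26 sCD14 measurements". The other four concern staying on product, prohibited medication, virologic failure, and intercurrent illness or vaccination.

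SAP 4.4 then says that, for all continuous outcomes, the summaries cover values at each study week and "change from baseline to post-baseline study weeks and will use the PP population". The sentence on between-arm comparison of mean changes follows directly and names no other set. Correlations are to be reported as the "Spearman correlation coefficient and associated p-value using the PP population".

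Protocol 9.6 has the same condition: "analyses will be as-treated, and limited to participants who 1) have baseline and week 26 sCD14 measurements". Neither document defines an evaluable set specific to an outcome.

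Three provisions limit the reach of the rule:

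- Safety is outside it: "Safety analyses will summarize the highest grade AE by participant using the mITT population".
- sCD14 is drawn twice at each end (entry and week 2; weeks 25 and 26). SAP 4.3 says "If only one result is available at either of these time points the single result will be used", and protocol 9.6 likewise says "a single measurement will be used rather than the average".
- On the other side, SAP 4.3 narrows which late draws count: "For per-protocol analyses the 'Week 25/26' calculation will only use results collected while on treatment".

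Protocol 9.6 also promises a supplemental intent-to-treat (ITT) analysis of all randomized participants. SAP 4.1 defines an ITT set, but SAP 4.4 assigns no analysis to it.

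**The concern.** Criteria 2 to 5 carry the as-treated rationale: they describe whether the participant received the intervention under clean conditions. Criterion 1 is different in kind. It is a data-availability rule for one endpoint, applied to all the others.

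The other outcomes need not fail when sCD14 fails. sCD14 is measured on stored plasma in a batch at the end of the study (protocol 6.3.15). Phenotyping uses stored PBMCs, the lipid profile uses stored serum, CD4 counts are available at interim reviews when the batched biomarkers are not (protocol 9.5), and bowel symptoms come from an assessment at the visit. Protocol 9.4 itself expects some missing data from laboratory complications.

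What is at stake is precision. SAP 3.2 lists 23 continuous secondary measures apart from microbiome diversity: 7 inflammation, KT ratio and coagulation, 2 translocation, 2 CD4, 3 monocyte, 6 activation, 2 senescence and 1 I-FABP. HOMA-IR, lipids, gastrointestinal symptoms and the week 26 to 38 changes are exploratory but fall under the same set. The microbiome measures are marked as not analysed at the statistical center, so it is unclear whether the SAP's PP set governs them.

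**Working it through.** **1. Reproduce the plan's own figures.** Inputs from protocol 9.4: difference 0.07 log10, SD of change 0.09, two-sided alpha 0.05, power 90%, 1:1 allocation, 20% inflation.

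- Two-sample t-test (noncentral t), standardized difference 0.07/0.09 = 0.778: 36 per arm, power 90.2%. The plan says 36 × 2 = 72.
- Inflation: 36/(1 − 0.20) = 45 per arm, 90 in total. This agrees.
- Secondary table at 36 versus 36: power 89.6%, 80.1% and 69.5% at 0.77, 0.67 and 0.59 SD, against a stated 90%, 80% and 70%. The 95% CI half-width is t(0.975, 70) × √(2/36) = 0.470 SD, against a stated 0.47.

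So the secondary table already assumes the 20% loss.

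**2. When does criterion 1 exclude someone?** One draw suffices at each time point. Exclusion needs both baseline draws missing, or no on-treatment draw at week 25/26.

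**3. How often?** The documents do not split missing data into sCD14-only loss and other loss. As an illustration, assume that each of the four assays is lost independently with probability q. Then

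P(excluded) = 1 − (1 − q²)²,

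and the standard error of another outcome measured in everyone rises by the factor 1/√(1 − P) = 1/(1 − q²).

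| q (assumed) | P(excluded) | Expected number of 90 | SE factor |
|---|---|---|---|
| 5% | 1 − 0.9975² = 0.5% | 0.4 | 1/0.9975 = 1.0025 |
| 10% | 1 − 0.99² = 2.0% | 1.8 | 1/0.99 = 1.010 |
| 20% | 1 − 0.96² = 7.8% | 7.1 | 1/0.96 = 1.042 |

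If any single missing assay excluded a participant, the figures would be 1 − (1 − q)⁴ = 18.6%, 34.4% and 59.0%. The single-result rule prevents that.

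**4. Outer bound on the gain from a fix.** Suppose that all of the 20% allowance were sCD14-only loss. Another marker would then have 45 rather than 36 per arm:

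- CI half-width 0.419 instead of 0.470 SD.
- Power at 0.67 SD 88% instead of 80%.
- Difference detectable with 80% power 0.60 instead of 0.67 SD.

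With 40 per arm the half-width is 0.445 SD and the power at 0.67 SD is 84%. The full bound is not realistic, because protocol 9.4 also attributes missing data to loss to follow-up, which removes all markers together.

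**5. Does the rule take the plan below its stated power?** Only if total loss exceeds 20%. At 32 per arm, for example, the half-width would be 0.50 SD and the power at 0.67 SD 75%.

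**6. Does the rule buy a common sample?** No. A participant with sCD14 but without a phenotype or KT result stays in the PP set and still contributes nothing to that outcome. The n can already differ by outcome, so the condition only removes data.

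**The case against.** The case against is substantial on size.

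- **sCD14 is rarely the limiting assay.** By the schedule of events, phenotyping, lipids, insulin resistance and KT ratio have one pre-treatment draw (week 2) and one at the end of treatment (week 26), while sCD14 has two of each. A missed week 2 or week 26 visit loses those markers and leaves sCD14 intact. The other soluble markers are stored plasma from largely the same visits, so losing a visit's plasma would usually remove them as well. This stands, and it is why the effect is small.
- **The two documents agree, and one fixed set is a recognized convention.** They do agree, so this is not an inconsistency. But the convention's usual benefit, the same people behind every result, is not delivered (step 6).
- **The protocol's ITT analysis would recover the data.** It carries no sCD14 condition. However, SAP 4.4 names only PP for continuous outcomes and correlations and mITT for safety. The SAP's rules for off-treatment results hint at some analysis outside the PP set, but none is specified.

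Four stronger readings are tempting, and the documents do not support them:

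- *Every outcome is gated.* Adverse events, a secondary outcome, use mITT.
- *One failed sCD14 assay excludes a participant.* A single result is enough at each time point.
- *Some 5% to 10% of the 72 evaluable participants are lost, raising standard errors by 2.6% to 5.4%* (1/√0.95 and 1/√0.90). No such rate is given, and the 72 are the evaluable sCD14 sample, so they already have the result.
- *Secondary power falls short of plan.* The 36 versus 36 table already absorbs a 20% loss.

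**Conclusion.** The point holds as a minor design inefficiency. As written, the plan discards valid data on other continuous outcomes for any participant without a usable sCD14 result at baseline or at week 25/26, and the SAP specifies no analysis that brings those data back.

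The likely cost is small: about 0.5% to 2.0% of participants, and 0.25% to 1.0% on standard errors, if assays are lost independently at 5% to 10%. Both the rates and the independence are assumptions. A shared storage or shipping failure of the sCD14 samples would make the loss larger, but could also remove other plasma markers. The primary sCD14 comparison and the sample size are not affected. This is a cheap improvement, not a threat to the trial's conclusions.

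**What to change.** In SAP 4.1 and in protocol 9.6, replace criterion 1 by a requirement to have the measurements needed for the outcome being analysed:

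- for the main comparison, baseline and an on-treatment week 25/26 result (or week 26, for outcomes measured only once);
- for the post-treatment change, week 26 and week 38;
- for a correlation, both markers at the time points concerned.

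Keep criteria 2 to 5 as they are, and report n per arm for each outcome.

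The cost is one phrase in each document. Changing only the SAP would create a discrepancy with the protocol. For sCD14 itself the new wording reduces to the present rule, so the primary analysis and the 90 participants stay as planned. The downside is that n will differ slightly between outcomes, as it already can.
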